Section 5.2 - Inclusion Criteria #2 Table 4 Objectives and Corresponding Endpoints Section 4.1 - Study Design	
Added additional details in the inclusion criteria regarding definition of “advanced” and “locally advanced.”
 
Specified that subjects in the dose escalation portion must be refractory to or intolerant of established therapies known to provide clinical benefit. Specified that subjects in the dose expansion portion must have received at least 2 prior lines of therapy for their hematological malignancy. Specified that subjects with MDS must be considered high or very high risk by IPSS-R.
	Clarification and addition in response to request by FDA
Section 4.1.1 - Part 1 (Dose Escalation) Table 6 mTPI-2 Decision Table for Dose Selection	
Revised text to end the study if DLT is observed in 1 of 3 subjects at the initial dose and included guidance on next steps if this occurs. Also moved this text to Section 6.2.2.2.
 
Updated the mTPI-2 table to include at DLT rate of 20% with an equivalence interval of 15% to 25%.
	Request by FDA
Section 8.1.3 - Dose-Limiting Toxicity	
Revised the DLT criteria to add the following:
 
 • Any Grade ≥ 4 nonhematologic toxicity • Any Grade ≥ 3 nonhematologic toxicity unless they resolve within 72 hours of onset • Grade 3 or 4 neutropenia lasting more than 7 days • Confirmed cases of Hy’s law 
For hematologic toxicities, neutropenia or thrombocytopenia that occurs with active leukemia may be excluded.
	Request by FDA
Section 6.2.2.2 - Stopping Rules for a Cohort or the Study Table 8 Bayesian Continuous Safety Monitoring Boundaries for n=15 (added)	Added formal rules for the dose expansion portion with Bayesian Continuous Safety Monitoring boundaries specifying that accrual in each respective cohort will be paused if the number of DLTs exceeds the threshold boundary and next steps will be determined based on SRC recommendations. The continuous safety monitoring rules have been revised based on a 20% DLT rate.	Request by FDA
Section 4.1.1 - Part 1 (Dose Escalation) Section 4.1.2 - Part 2 (Dose Expansion) Section 1.1 - Synopsis	Removed language allowing investigator discretion in decisions allowing patients to continue or discontinue treatment based on investigator judgment of whether or not subjects are benefiting from treatment.	Request by FDA
Section 5.2 - Inclusion Criteria #7	Revised inclusion criterion for creatinine clearance to ≥ 60 mL/min for both dose escalation and dose expansion.	Request by FDA

Section Number	Summary of Change	Rationale for Change
Section 5.2 - Inclusion Criteria #5	Revised text to specify that AITL subjects must have a platelet count $\geq 20,000/\mu\text{L}$ for eligibility; however, platelet transfusions are permitted to reach this level.	Request by FDA
Section 7.4.2 - Permitted Therapies	Added a link to the treatment of differentiation syndrome.	Request by FDA
Section 7.4.3 - Drug-Drug Interactions	Added text to specify close and frequent monitoring of adverse events with concomitant use of any medication that is a substrate of CCI and has a narrow therapeutic index.	Request by FDA
Section 7.5.1 Adjustment of Dose within the DLT Assessment Window	Revised to eliminate the option to restart study drug after Grade 4 events. Deleted text allowing subjects to continue treatment if an AE does not meet the DLT criteria or is a Grade 3 or 4 non-DLT.	Request by FDA
Section 7.5.2 - Dose Adjustment Outside the DLT Assessment Window (Including Dose Expansion Part) Table 9 Dose Adjustment for Hematologic Toxicity (added) Table 10 Dose Adjustment for Nonhematologic Toxicity (added)	Revised the guidance for dose adjustment for hematologic and nonhematologic toxicity outside the DLT assessment window with addition of new tables for dose adjustment.	Request by FDA
Section 7.5.3 - Intra-Dose Escalation (deleted section)	Deleted provision for allowing intra-subject dose escalation.	Request by FDA
Section 7.6.1 - Differentiation Syndrome Handling Principles	Added text stating the following: 
Hemodynamic monitoring will also be performed with dexamethasone administration.HMPL-306 will be interrupted in the event of severe pulmonary symptoms or renal dysfunction. Revised condition under which HMPL-306 may resume to specify resumption will occur after symptoms improve to Grade 2 or lower.	Request by FDA
Section 7.6.2 - Handling Principles for Noninfectious Leukocytosis (revised heading)	
Defined noninfectious leukocytosis as $\text{WBC} > 25 \times 10^9/\text{L}$ or an absolute increase in total WBC of $> 15 \times 10^9/\text{L}$ from baseline.Specified that resuming study drug WBC count should be $< 30 \times 10^9/\text{L}$ in addition to resolution of clinical features of differentiation syndrome.	Request by FDA

Section Number	Summary of Change	Rationale for Change
Section 7.6.2 - Handling Principles for Noninfectious Leukocytosis (revised heading)	Revised hydroxyurea oral therapy instructions to align with institutional standards.	Clarification
Section 7.5.3 - Dose Adjustment for QT Interval Prolongation (section added) Table 11 Dose Adjustment for QT Interval Prolongation (table added)	Added guidance for dose adjustment for QT interval prolongation.	Request by FDA
Section 6.1.10.4 - Blood Chemistry	Added uric acid to list of blood chemistry tests.	Request by FDA
Section 6.1.9 - Ophthalmologic Examination	Added OCT to list of ophthalmic examinations. Specified dose adjustments required if RPE detachment is noted.	Request by FDA
Appendix 1 PK/PD/Biomarker/ECG Assessments for Escalation Cohorts Appendix 2 PK/PD/Biomarker/ECG Assessments for Expansion Cohorts Section 4.2.3 - Rationale for Biomarker Testing	Added mutational analysis for CCI [REDACTED].	Request by FDA
Section 6.2.1.1 - Permanent Discontinuation of Treatment	Revised conditions for permanent discontinuation of treatment to specify that all patients may receive a maximum of 6 treatment cycles. Defined conditions under which patients may not receive the maximum number of treatment cycles.	Request by FDA
Section 7.5.2 - Dose Adjustment Outside the DLT Assessment Window (Including Dose Expansion Part)	Specified that dose adjustments are to be made for any adverse event deemed at least possibly related to HMPL-306.	Request by FDA
Section 7.5.3 - Dose Adjustment for QT Interval Prolongation Table 11 Dose Adjustment for QT Interval Prolongation	Modified the dose adjustment for QTc prolongation based on the USPI for ivosidenib.	Request by FDA
Section 4.2.2 - Rationale for Study Population Selection	Added text and references to clarify rationale for use of HMPL-306 for treatment of MDS, MPN, and AITL.	Suggestion by FDA

Section Number	Summary of Change	Rationale for Change
Table 3 Summary of Potential Risks of HMPL-306	Changed frequency of WBC monitoring from weekly in Cycle 2 to every other week in Cycle 2. Removed text “medication” from “patient medication guide.”	To align with the schedule of events To align with operational conduct of the trial
Appendix 4 COVID-19 Risk Assessment	Remove text “#5.”	Correct discrepancy with exclusion criterion #

LIST OF ABBREVIATIONS

Abbreviation	Term
2-HG	2-Hydroxyglutaric acid
AE	Adverse event
AESI	Adverse event of special interest
AITL	Angio-immunoblastic T-cell lymphoma
ALP	Alkaline phosphatase
ALT	Alanine aminotransferase
AML	Acute myeloid leukemia
ATC	Anatomic therapeutic classification
BMI	Body mass index
BP	Blood pressure
CBR	Clinical benefit rates
CI	Confidence interval
COVID-19	Coronavirus disease 2019
CR	Complete response
CR _{MRD}	Complete response with negative minimal residual disease
CRi	Complete response with incomplete count
CRh	Complete response with partial hematological recovery
CRF	Case report form
CTCAE	Common terminology criteria for adverse events
DBP	Diastolic blood pressure
DFS	Disease-free survival
DLT	Dose-limiting toxicity
DOCR	Duration of CR
DoR	Duration of response
ECG	Electrocardiogram
ECOG	Eastern cooperative oncology group
ECHO	Echocardiogram
EFS	Event-free survival
GCP	Good clinical practice
ICH	International council on harmonization
IDH	Isocitrate dehydrogenase
IWG	International working group
LLQ	Lower limit of quantification
MDS	Myelodysplastic syndrome
MedDRA	Medical dictionary for regulatory activities
MLFS	Morphologically leukemia-free state
mTPI-2	Modified toxicity probability interval-2
MUGA	Multiple-gated acquisition
NCI	National cancer institute
MTD	Maximum tolerated dose
ORR	Objective response rate

Abbreviation	Term
OC	Observed case
OS	Overall survival
PD	Progressive disease
PFS	Progression-free survival
PK	Pharmacokinetic
PO	Oral(ly)
PR	Partial response
PS	Performance status
PT	Preferred term
QD	Once daily
QTcF	QT interval corrected by the method of fredericia
RBC	Red blood cell
RP2D	Recommended phase 2 dose
SAE	Serious adverse event
SAP	Statistical analysis plan
SAS	Statistical analysis software
SBP	Systolic blood pressure
SD	Stable disease
SOC	System organ class
SRC	Safety review committee
TD	Transfusion dependence
TEAE	Treatment-emergent adverse event
TI	Transfusion independence
TPR	Timepoint response
TTCR	Time to CR
TTR	Time to response
WBC	White blood cell
WHO-DD	World health organization drug dictionary

1. INTRODUCTION

This statistical analysis plan (SAP) describes the planned statistical analyses and data presentations for study 2020-306-GLOB1. The SAP is based on the Protocol Version Amendment 5 (dated 02 Nov 2023) and CRF version 8 (dated 11 Sep 2024).

Study measurements and assessments, planned statistical methods, and derived variables are summarized in this plan. Planned tables, figures, and listings are specified. All decisions regarding final analyses, as defined in this SAP document, have been made prior to locking the database. Any deviations from these guidelines will be documented in the clinical study report (CSR).

In the protocol, though patients with high-risk myelodysplastic syndrome (MDS) and angio immunoblastic T cell lymphoma (AITL) were also planned to be enrolled to the study, in reality, there were no patients with MDS and AITL enrolled into the study. Therefore, the analysis of the study will be focused only on AML patients from dose escalation part and dose expansion part.

The analyses related to pharmacokinetic (PK) endpoints will be described in a separate analysis plan.

2. STUDY DETAILS

2.1 Study Objectives

The objectives and corresponding endpoints are summarized in [Table 1](#).

Table 1 Objectives and Corresponding Endpoints

Tier	Objectives	Endpoints
Primary	Part 1 – Dose Escalation: To evaluate the safety and tolerability of HMPL-306 in patients with advanced hematological malignancies that harbor isocitrate dehydrogenase (IDH) mutations.	
• Maximum tolerated dose (MTD) and/or recommended phase 2 dose (RP2D)• Safety including dose-limiting toxicities (DLTs), treatment-emergent adverse events (TEAEs), serious adverse events (SAEs), deaths, electrocardiograms (ECGs), and clinical laboratory abnormalities
	Part 2 – Dose Expansion: To characterize safety and tolerability and to determine RP2D of HMPL-306 in patients with advanced hematological malignancies that harbor IDH mutations.	
• Safety including DLTs, TEAEs, SAEs, deaths, ECGs, and clinical laboratory abnormalities
Secondary	To assess preliminary antitumor activity of HMPL-306 in patients with advanced hematological malignancies that harbor IDH mutations.	
• Best overall response (BOR), objective response rate (ORR), time to response (TTR), duration of response (DoR), clinical benefit rate (CBR), progression-free survival (PFS), overall survival (OS), disease free survival (DFS), event-free survival (EFS), and post-baseline transfusion independence
	To assess pharmacokinetics (PK) of HMPL-306 in patients with advanced hematological malignancies that harbor IDH mutations	
• Observed plasma concentrations and drug exposure parameters of HMPL-306
	To assess pharmacodynamics (PD) of HMPL-306 in patients with advanced hematological malignancies that harbor IDH mutations	
• Observed plasma concentrations of 2-hydroxyglutaric acid (2-HG)
Exploratory	To explore relationships between changes in frequency of genetic mutations, efficacy, PK, PD and safety after HMPL-306 treatment	
• Changes from baseline in tumor markers, correlation with drug exposure, target engagement and efficacy and safety outcomes
	To explore relationships between HMPL-306 PK drug exposure, target engagement (TE), 2-HG levels, and percentage inhibition	

To explore the influence of genetic abnormalities (other than IDH mutations) on safety, efficacy, PD, PK, and clinical response to HMPL-306 treatment.

2-HG = 2-hydroxyglutaric acid; CBR=clinical benefit rate; DFS=disease-free survival; DLT = dose-limiting toxicity; DoR=duration of response; ECG = electrocardiogram; EFS=event-free survival; IDH = isocitrate dehydrogenase; MTD = maximum tolerated dose; ORR=objective response rate; OS=overall survival; PD = pharmacodynamics; PK = pharmacokinetics; PFS=progression-free survival; PR=partial response; RP2D = recommended phase 2 dose; SAE = serious adverse event; SD=stable disease; TEAE = treatment emergent adverse event; TTR=time to response.

2.2 Study Design

This is a phase 1, open-label, multicenter, single-arm study to evaluate safety, tolerability, PK, PD and preliminary efficacy of HMPL-306 administered orally in treatment of patients with advanced relapsed, refractory, or resistant hematological malignancies that harbor IDH mutations. The study consists of 2 parts: dose escalation part (Part 1) and dose expansion part (Part 2).

The first part of the study is dose escalation, where cohorts of patients will receive ascending oral doses of HMPL-306 to determine MTD and/or the RP2D. The modified toxicity probability interval-2 (mTPI-2) ([Greenberg 2012](#), [Guo 2017](#)) design will be used to perform dose escalation and MTD/RP2D determination. Briefly, the mTPI-2 method uses a Bayesian framework and a hierarchical model to compute the dose escalation based on the interval between the toxicity rate of each dose level and target probability ([Greenberg 2012](#), [Guo 2017](#)). This study is designed targeting a DLT rate of 20% with an equivalence interval of 15% to 25%.

Seven days prior to initiating daily administration of HMPL-306 from Cycle 1 Day 1 (C1D1), patients enrolled in each cohort during dose escalation will be administered a single oral dose of HMPL-306 on Day -7 relative to C1D1 (Day 1 of PK week). Serial blood samples will be collected from Days 1 to 7 of the PK week for analysis of plasma concentrations of HMPL-306 and 2-HG.

A cycle of study treatment is defined as 28 days of continuous daily dosing. After the PK week, dose escalation will start at **[REDACTED]** mg QD orally (PO) for Cohort 1 and then escalate in the sequence of **[REDACTED]** mg QD, and **[REDACTED]** mg QD.

Safety monitoring and evaluation of dose escalation will be carried out by the Safety Review Committee (SRC), which is comprised of the sponsor and investigators.

[figure not shown]
In the dose-expansion part, 1 cohort of patients will receive HMPL-306 at MTD and/or RP2D to evaluate further the safety, tolerability, PK, PD, and preliminary efficacy in approximately 10 patients with advanced relapsed, refractory, or resistant hematological malignancies with IDH mutations. Patients enrolled in the dose expansion part must not have standard therapeutic options available (including IDH inhibitors where approved) and must have the following:

- Relapsed AML unsuitable for intensive chemotherapy or venetoclax-based regimen or target agents;
- Primary refractory AML unsuitable for intensive chemotherapy or venetoclax-based regimen or target agents;
- Relapsed/refractory AML that has progressed on prior IDH treatment

The sponsor, in consultation with SRC, may decide to increase or decrease the number of enrolled patients in each cohort, depending on preliminary clinical response, safety signals, or operational feasibility. Patients who are not efficacy evaluable in any cohort may be replaced.

The overall study schema is presented in [Figure 1](#).

Figure 1 Study Schema

Any patient who discontinues treatment should be encouraged to return to the study site for an End of Treatment (EOT) Visit and continue with the remaining study visits. Patients must be discontinued from treatment for disease progression, withdrawal of consent, intolerable toxicity, repeated non-compliance or poor compliance, commencement of other antitumor treatment during the study, pregnancy, loss to follow-up, termination of the study by the sponsor, death, or end of the study.

Patients who discontinue the study drug due to reasons other than disease progression, death, lost to follow-up, or withdrawal of consent will remain on study for tumor assessments and will be followed every 12 weeks (± 14 days) from the EOT visit or last assessment, until disease progression, initiation of new anticancer therapy, withdrawal of consent, lost to follow-up, death, conditions are met, or the end of the study, whichever comes first. Survival information can be obtained via phone and information will be documented in the source documents and relevant case report forms (CRFs). The end of study is defined as the date on which all patients have their last visit or 1 year after the last patient has their first visit, whichever comes first.

2.3. Determination of Sample Size

Approximately 40 to 50 patients are to be enrolled in this study (approximately 24 to 30 evaluable patients are expected in the dose-escalation part and approximately 10 patients are estimated for the dose expansion part).

2.3.1. Dose Escalation Part

The maximum sample size in this part will be determined jointly by the sponsor and investigator. The exact sample size of mTPI-2 design in dose escalation part cannot be pre-specified due to dynamic nature of Bayesian allocation procedure. Patients not evaluable for DLT may be replaced, and this may result in the number of patients enrolled being more than expected. An estimated 24 to 30 evaluable patients may be enrolled in this part.

2.3.2. Dose Expansion Part

To better describe the safety of the recommended single-dose of HMPL-306 for future studies, approximately 10 AML patients are expected to be treated with HMPL-306 at this part. For a given adverse event (AE) with a true rate of 10%, 5%, or 1%, the probability of observing at least 1 AE in 10 patients is 65%, 40%, and 9.6%, respectively.

Assuming that the true complete response (CR) rate is 20%, then the probability that at least 1 case of CR is observed in a cohort of 10 patients is 89%, the probability that at least 2 cases of CR are observed is 62.4%, and the probability that no CR is observed is 11%. If further evaluation of safety and efficacy signals is warranted, then more patients may be enrolled in the dose expansion cohort.

3. ANALYSIS SETS

3.1. Definition of Analysis Sets

Data analyses will be based on the analysis sets defined below. Unless otherwise specified, analyses will be conducted on the basis of first dose level of study drug that a patient received.

3.1.1. All Subject Set

All patients who signed the informed consent (including pre-screening and screening informed consent).

3.1.2. Safety Analysis Set

All enrolled patients who received at least 1 dose of study drug (HMPL-306) will be included in safety analysis population. This is the primary analysis set for safety analysis.

3.1.3. DLT-Evaluable Analysis Set

The DLT-evaluable analysis set includes all patients provided by HUTCHMED clinical team based on the decision made with the SRC after SRC meeting for each cohort during the dose escalation phase.

DLT analysis for the Part 1 dose escalation phase will be performed using the DLT evaluable analysis set.

3.1.4. Efficacy Analysis Set

All enrolled patients who received at least 1 dose of study drug from C1D1 in continuous cycle (i.e. excluding single oral dose from the PK week for the dose escalation part) will be included in efficacy analysis population. This is the primary analysis set for efficacy analysis.

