2.3 Benefit/Risk Assessment

2.3.1 Benefit-Risk Assessment

The patients to be enrolled in this study will be those with advanced, relapsed, refractory, or resistant hematological malignancies and, therefore, have an unmet medical need.

For patients with refractory AML, the median overall survival (OS) is approximately 1.5 months with only 8% one-year survival (Gale 2008, Giles 2005). National Comprehensive Cancer Network (NCCN) and European Society for Medical Oncology (ESMO) practice guidelines recommend considering clinical trial for patients with primary refractory AML (NCCN-AML 2021, Heuser 2020). In the event that no clinical trial is available, then the intent of a second salvage chemotherapy in these patients, however, is only supportive at best. Therefore, patients with AML who have received at least 2 prior lines of therapy do not have a viable

treatment option available. Additionally, AML patients who fail IDH inhibitor therapies do not have any standard treatment options available, making them a population with very high unmet need ([NCCN-AML 2021](#)).

High-risk MDS (HR-MDS) carries a major risk of progression to AML and short survival. There are no standard treatment options for patients with relapsed or refractory HR-MDS. Patients ineligible for allo-HSCT have no approved second-line treatment options after failure of an approved hypomethylating agent (HMA), and clinical trials are the recommended option as per NCCN and ESMO guidelines ([NCCN-MDS 2021](#), [ELN 2017](#), [Fenaux 2020](#)).

Similarly, ESMO and NCCN practice guidelines recommend considering clinical trial for patients with relapsed or refractory AITL because of the poor survival rate with available single agent palliative therapy options ([NCCN-MDS 2021](#), [NCCN-PTCL 2021](#), [d'Amore 2015](#)).

HMPL-306 is a dual inhibitor of IDH1 and IDH2, which, in preclinical studies, has demonstrated similar efficacy to single target IDH inhibitors (ivosidenib and enasidenib), and may have similar benefit to other IDH1 and/or IDH2 inhibitors in the same class. Preclinical studies, including toxicology studies, indicate that HMPL-306 is well tolerated. Additionally, there are no approved therapies for the treatment of hematological malignancies that have been previously treated with an mIDH1 or mIDH2 inhibitor, thus providing a potential treatment option in an area of unmet medical need.

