6.1.2 PK Week

The PK week is defined as 7 days prior to C1D1 where a single dose of HMPL-306 will be administered on Day 1 of PK week (Day -7 relative to C1D1). Blood samples and ECG assessments will be collected at intervals as specified in [Appendix 1](#). These samples will be analyzed for plasma concentrations of HMPL-306, 2-HG, and other biological markers as defined by the sponsor. PK week is applicable to every cohort in the dose escalation part only. See [Appendix 1](#) for more details. PK week for a particular dose cohort will be considered optional and not mandatory if PK week data from 5 patients have been collected at the same dose.

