9.1.3 Analysis Sets

The following analysis sets are defined for this study:

- Safety analysis set: All enrolled patients who received at least 1 dose of study treatment will be included in safety analysis population. Safety evaluation will be performed based

on first dose of study treatment received by a patient. This is the primary population for safety and efficacy analyses.

- DLT-evaluable analysis set: All patients enrolled in dose escalation part who are evaluable for DLT assessment. A patient is DLT-evaluable if such a patient meets the following criteria:
 - Has received at least 75% of the assigned dose of study drug during DLT assessment window
 - OR
 - Has not completed the DLT assessment period due to a DLT
- Response (efficacy) evaluable analysis set: All patients who receive study treatment and have a baseline tumor assessment, followed by at least 1 post-baseline assessment (usually after C3D1) will be considered evaluable for antitumor clinical response or efficacy endpoints.
- PK analysis set: All patients with at least 1 quantifiable plasma concentrations of HMPL-306 will be included in PK population analysis.
- PD analysis set: All patients with at least 1 quantifiable level of 2-HG in plasma will be included in PD population analysis.

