9.2.7 Efficacy Analysis

Tumor assessment for patients with AML, HR-MDS, or AITL will be evaluated by the investigator according to the specific guidelines outlined in Section 9.2.7.1. However, the efficacy analysis will only be conducted for AML patients; for patients with HR-MDS or AITL, if enrolled, the tumor assessment data will be listed.

The following efficacy endpoints will be derived and analyzed using the safety analysis set for patients with AML:

- OS: defined as the time from the start of the study drug until death from any cause.
- Progression-free survival (PFS): defined as the time from the start of study treatment to disease progression, or death due to any cause, whichever occurs first.
- Baseline transfusion dependence: transfusions of red blood cells (RBCs) or platelets within 28 days prior to the first dose of treatment.
- Post-baseline transfusion independence (summarized through the following 2 ways):
 - No RBC or platelet transfusion for at least ≥ 4 weeks during treatment period; or
 - No RBC or platelet transfusion for at least ≥ 8 weeks during treatment period.

Patients with AML treated at the RP2D from Part 1 will be included in the data summary of the cohort in Part 2, unless otherwise specified. A patient data listing will be prepared for all patients.

Tumor response endpoints as defined in Section 9.2.7.1 (eg, best overall response, objective response rate [ORR], clinical benefit rate [CBR], and duration of response [DoR]) will be analyzed using the safety analysis set. For binary response endpoints such as ORR and CBR, the estimate and its 95% CI will be calculated using the Clopper-Pearson method for each cohort. The response (efficacy) evaluable analysis set will be used to conduct sensitivity analysis for tumor response.

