5.2.9. Efficacy Analyses

All efficacy analyses will be based on the efficacy analysis set. The response evaluable analysis set will be used to conduct sensitivity analysis for tumor response.

No formal comparison or hypothesis testing is planned for this study. Two-sided 95% confidence intervals (CIs) will be calculated in the applicable summary, unless otherwise specified.

Main efficacy analysis will be repeated by IDH naïve and treated status based on efficacy analysis set.

All efficacy data will be listed.

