7. CHANGE FROM THE PROTOCOL

Here is a list of changes in this analysis plan compared with the protocol

- Added All Subject Set for pre-screening and screening summaries.
- Added Efficacy Analysis Set as primary analysis set for efficacy analysis and clarified definition of Response Evaluable Analysis Set as single dose from the PK week might not be an effective treatment. Safety Analysis Set was the primary set for safety analysis.
- The DLT- evaluable analysis set definition in the protocol is to include all patients enrolled into dose escalation part of the study who (i) either received at least 75% of the assigned doses of the HMPL-306 during the DLT assessment window (i.e. Cycle 1 Day 1 [C1D1] through C1D28) or (ii) experienced a DLT in Cycle 1. However, since these criteria have been incorporated in the SRC review, the DLT-evaluable analysis set will be based on the decision from the SRC review.
- Removed DLT-equivalent analysis as investigator's evaluation of each AE satisfying DLT criteria or not was not well documented in EDC.
- Patients enrolled were summarized based on all subject set instead of safety analysis set.
- Removed Rate of CR+CRh, duration of CR+CRh and time to CR+CRh endpoints, since cCR-2 (rate of CRM RD+CR+CRh) and cCR-3 (rate of CRM RD+CR) are more meaningful.
- Removed Time to Hematologic Recurrence endpoint as it has the similar rationale for DOcCR1.
- Removed Disease Free Survival (DFS) endpoint as it has the same rationale for DOcCR1.

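### The SAP's primary efficacy set leaves Part 1 patients who took only the PK-week dose out of the response denominators, and no planned efficacy analysis puts them back

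*SAP*

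**What the plan says.** Protocol 9.1.3 defines the safety analysis set as enrolled patients with at least one dose and adds: "This is the primary population for safety and efficacy analyses". Protocol 9.2.7 repeats this for OS, PFS and transfusion endpoints ("The following efficacy endpoints will be derived and analyzed using the safety analysis set for patients with AML") and names the same set for tumour response. It measures OS and PFS from the start of study drug.

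SAP 3.1.4 defines a new primary efficacy set: "All enrolled patients who received at least 1 dose of study drug from C1D1 in continuous cycle", with the qualifier "excluding single oral dose from the PK week for the dose escalation part". SAP 5.2.9 then states: "All efficacy analyses will be based on the efficacy analysis set". The only sensitivity set, the Response Evaluable Analysis Set (SAP 3.1.5), is restricted to members of the efficacy set. Best overall response, time to response, EFS, OS and PFS all start at the first Cycle 1 dose (SAP 4.2.1 and 4.2.4 to 4.2.7).

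SAP section 7 discloses the new set and gives as its reason that a "single dose from the PK week might not be an effective treatment". It does not mention that the origin of OS and PFS has moved from the start of study drug to Cycle 1.

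**The concern.** In Part 1 the PK-week dose is given seven days before C1D1. Whether a treated patient enters the primary efficacy set therefore depends on what happens after that first dose: death, toxicity, progression or withdrawal in that week removes the patient. For a response rate this works in one direction, because the patients removed have no chance of being counted as responders.

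The efficacy data come almost entirely from Part 1. The footnote to SAP Table 13 says only one Part 2 patient was enrolled, and that patient is pooled into Cohort 8. Efficacy is reported by dose level, where one patient more or less in the denominator moves the percentage visibly. A reader who expects the protocol's all-treated rate would find no table that gives it.

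**Working it through.** **The plan's own figures.** The documents give no figure for the number of PK-week-only patients. The nearest computable figures are the Part 2 probabilities in Protocol 9.1.2.2 and SAP 2.3.2, for a 20% CR rate and n = 10. They reproduce: no CR 0.8^10 = 0.107 (stated 11%), at least one 0.893 (89%), at least two 0.624 (62.4%). The point does not rest on them; only the 20% rate is borrowed below, as an assumption.

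**Step 1: can a dropped patient be a responder?** SAP 4.2.1 builds best overall response from time-point responses dated from the first Cycle 1 dose. A patient with no Cycle 1 dose has none. ORR, CBR and the composite CR categories are all derived from best overall response (SAP 4.2.2). So with x responders, N treated and k PK-week-only patients, the protocol rate is x/N and the SAP rate is x/(N − k), which is never lower.

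**Step 2: size, with k assumed.**

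| Treated N, responders x | k = 0 | k = 1 | k = 2 | k = 3 |
|---|---|---|---|---|
| 30, 6 | 20.0% | 20.7% | 21.4% | 22.2% |
| 24, 5 | 20.8% | 21.7% | 22.7% | 23.8% |

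The Clopper-Pearson 95% interval for the first row goes from 7.7–38.6% (k = 0) to 8.6–42.3% (k = 3). The 24 to 30 in the plan counts evaluable patients, with replacements enrolled on top. If 30 is instead the number left after three exclusions, the contrast is 6/33 = 18.2% against 6/30 = 20.0%, a similar gap.

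**Step 3: a single dose level.** Protocol 4.1.1 requires at least three patients per level. Its DLT window runs from C1D1 to C1D28 and does not count the PK-week dose. A PK-week-only patient is therefore not DLT-evaluable and may be replaced. With three evaluable patients plus one replaced patient, one responder gives 1/4 = 25.0% on the protocol set and 1/3 = 33.3% on the SAP set.

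**Step 4: does the stated reason fit the rule?** A patient who takes one dose on C1D1 and stops is in the efficacy set. A patient who takes one dose in PK week and stops is out. If one dose may be ineffective, it may be so in both cases. SAP 4.2.1 also assigns progressive disease to a patient without a post-dose tumour assessment who dies before the second one was due, so an early death after C1D1 counts as a failure, while a death a few days sooner disappears from the denominator. The reason supports starting the clock at C1D1; it does not support the smaller denominator.

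**Step 5: OS and PFS.** Here both the set and the clock move to C1D1. The quantity estimated becomes S(t + 7 days)/S(7 days), which is survival given that C1D1 was reached. Under a constant hazard this ratio equals S(t), so the curve is unchanged. Under other hazards it could move either way.

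**The case against.** The strongest defence has four parts.

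- **The change is disclosed, and the patients do not vanish.** SAP section 7 lists the new set with a reason. SAP 5.2.1 plans a table of exclusions from each set with reasons, and the safety, death and disposition summaries keep these patients. This stands, but none of it is an efficacy result on the protocol's population.
- **One entry rule and one clock for everyone is coherent.** Under Protocol 6.1.2, "PK week for a particular dose cohort will be considered optional and not mandatory if PK week data from 5 patients have been collected" at that dose, and Part 2 has no PK week, so measuring from first continuous dose treats all patients alike. This stands as an argument for the C1D1 clock. It also answers a reader who might infer that patients within one dose level are selected by different rules.
- **OS and PFS are not shown to be inflated.** A reader might infer that dropping PK-week patients removes early deaths and so raises OS. The documents do not support that: the origin moves with the set, and a patient may miss C1D1 through withdrawal or toxicity and be alive, since Protocol 6.1.19 follows all patients for survival.
- **The number may be zero.** Protocol 2.3.1 says that for refractory AML "the median overall survival (OS) is approximately 1.5 months with only 8% one-year survival". A reader might turn this into an expected count: with exponential survival, 1 − 0.08^(7/365.25) = 4.7% to 1 − 0.5^(7/45.66) = 10.1% would die within seven days, or about 1 to 3 of 24 to 30 patients. That is not a usable estimate. The survival figures describe a background population, whereas eligibility here requires ECOG 0 to 2 and excludes immediately life-threatening complications. The base of 24 to 30 also counts evaluable patients, which PK-week-only patients are not.

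It is also fair that efficacy is secondary and that no hypothesis is tested.

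**Conclusion.** The point holds for response rates. The SAP departs from the protocol's all-treated efficacy population, the departure can only leave ORR, CBR and the composite CR rates unchanged or raise them, and no planned efficacy analysis, primary or sensitivity, retains the excluded patients. Only Part 1 patients given a PK-week dose can be affected.

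The size depends on a count the documents do not give. If it is zero, nothing changes. At an assumed response rate of about 20%, one to three exclusions from 30 treated patients add 0.7 to 2.2 percentage points overall; one exclusion in a level of four treated patients with one responder adds about 8 points.

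For OS and PFS the finding is narrower: the estimand is now survival conditional on reaching C1D1, the direction of any difference is not established, and section 7 omits the change of origin. A death in PK week would appear in the death summary but not in OS.

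**What to change.** 1. Report ORR, CBR and the composite CR rates on the Safety Analysis Set, as the protocol specifies, with PK-week-only patients counted as non-responders. Preferably make this primary and the C1D1 set the sensitivity analysis; at minimum, plan it as a sensitivity analysis.
2. Add a sensitivity analysis of OS and PFS on the Safety Analysis Set, measured from first dose for every patient. SAP 4.1.1 already defines that date as the safety reference start. Do not mix origins, with first dose for PK-week-only patients and C1D1 for the rest. That keeps PK-week deaths but discards the survivors' first week. With a 1.5-month median and constant hazard, 3-month OS is 25%, and the mixed curve would give 0.899 × 25% = 22.5%.
3. List the change of OS and PFS origin in SAP section 7.

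The cost is some SAP wording and one repeat run of existing tables on a set that is already defined. Response rates may come out slightly lower.
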